2 ELIGIBILITY ASSESSMENT AND ENROLLMENT

2.1 ELIGIBILITY CRITERIA

2.1.1 Inclusion Criteria

- 2.1.1.1 Patients must have histologically confirmed solid tumor malignancy for which no curative therapy exists.
- 2.1.1.2 Pancreatic adenocarcinoma, extrahepatic cholangiocarcinoma or epithelioid subtype of mesothelioma, as determined by NCI Laboratory of Pathology, OR for all other tumor types, at least 20% of tumor cells must express mesothelin. Determination can be made using archival tumor tissue or fresh biopsy if archival tumor tissue is not available.
- 2.1.1.3 All patients must have evaluable disease (i.e. measurable per RECIST 1.1. or by following CA19-9 tumor marker). Patients in the expansion cohort must have measurable disease, per RECIST 1.1. See Section 6.3 for the evaluation of measurable disease.
- 2.1.1.4 Patients must have received at least one prior standard systemic treatment regimen for advanced disease OR be ineligible to receive available standards due to co-morbidities, prior toxicity, lack of standard options for tumor type, or having received all standards

available for prior treatment of early stage disease OR have refused first-line standard systemic treatment but have received prior anti-cancer treatments.

- 2.1.1.5 Patients with dMMR/MSI-H disease must have received at least one prior anti-PD1 therapy, be ineligible to receive this treatment due to concurrent medical conditions, or have refused this therapy.
- 2.1.1.6 ECOG performance status (PS) 0-2 (Appendix A- Performance Status Criteria).
- 2.1.1.7 Age ≥18 years. Because no dosing or adverse event data are currently available on the use of LMB-100 alone or in combination with tofacitinib in persons with <18 years of age, children are excluded from this study.
- 2.1.1.8 Patients must be more than 14 days removed from most recent minor surgical procedure (such as biliary stenting), 28 days from most recent major surgical procedure and 14 days from radiation therapy, systemic treatments (such as chemotherapy), or experimental drug treatment. All acute toxicities from prior treatment must have resolved to grade 1 or less except alopecia, anemia, peripheral neuropathy, or endocrinopathies corrected by replacement therapy.
- 2.1.1.9 Adequate hematological function: neutrophil count of $\ge 1.5 \times 10^3$ cells/µL, platelet count of $\ge 85,000/\mu$ L, hemoglobin ≥ 9 g/dL
- 2.1.1.10 Serum albumin \geq 2.5 mg/dL without intravenous supplementation

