2.2.2 Screening activities performed after a consent for screening has been signed

For patients requiring testing for MSLN expression (see Section 2.3.1), screening will occur on this study. For all other subjects, screening will occur on study 01-C-0129.

The following activities will be performed only after the subject has signed the appropriate consent for screening. They will be performed within 28 days before registration for study treatment unless specified:

- Assess tumor MSLN expression by immunohistochemistry analysis in archival tissue or fresh biopsy samples ONLY for patients who do not have a diagnosis of epithelioid mesothelioma, extrahepatic cholangiocarcinoma or pancreatic adenocarcinoma.
- Medical History and physical exam
- Vital signs including ambulatory oxygen saturation by pulse oximetry
- ECOG performance status
- Pregnancy test in women of childbearing potential (within 7-days prior to initiation of study therapy)
- ECG
- Echocardiogram
- CT scan of chest, abdomen and/or pelvis and areas of known or suspected disease involvement; MRI and/ or PET scan may also be performed when appropriate per PI discretion.
- CBC with differential, Acute Care Panel (sodium, potassium, chloride, bicarbonate, creatinine, glucose, BUN), Hepatic Panel (alkaline phosphatase, AST, ALT, total bilirubin, direct bilirubin), Mineral Panel (albumin, calcium, magnesium, phosphorus), creatine kinase, C-reactive protein, 1,25-dihydroxy vitamin D, Coagulation (PT, PTT), lactate dehydrogenase
- CA 19-9 serum tumor marker for pancreatobiliary cancer patients, or other appropriate tumor marker in other tumor types
- Testing for HIV, HCV, HBV: anti-HIV antibody, Anti-HCV Antibody, HBs Ag Screening
- Screening for latent tuberculosis by interferon-x release assay: QuantiFERON-TB Gold Plus or similar
- Urinalysis

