3.1.3 Treatment Extension

Participants who complete 3 cycles of therapy with LMB-100/tofacitinib and appear to be deriving clinical benefit as evidenced by lack of progression on CT scan and decreasing serum tumor marker (in patients with serum tumor marker that has historically followed their disease trend) may continue to receive additional cycles of treatment at the discretion of the PI until unacceptable toxicity or patient is no longer thought to be benefiting, or PI's decision to discontinue treatment. If a participant is offered treatment extension but refuses, he/she will be removed from protocol therapy. Participants offered treatment extension may defer immediate treatment with study drugs to take a treatment holiday or to receive other intervening treatments (including investigational treatments). If a participant chooses to defer treatment extension beyond 6 weeks or to have a different intervening therapy, the PI may require to repeat some screening safety evaluations before reinitiating LMB-100/tofacitinib and will require washout periods and criteria consistent with those described in Sections 2.1.1.8, 2.1.1.9 and 2.1.1.10. Safety monitoring while receiving treatment extension will continue as described in the Study Calendar. Limited research labs will be taken as described in Sample Collection Schedule (Section 5.2).

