3.2.3 Schematic view of the administration set-up

3.3 DOSE MODIFICATIONS

3.3.1 LMB-100

LMB-100 infusion may be held for up to 48 hours due to drug-associated toxicity or adverse events from other intercurrent medical conditions (such as primary cancer diagnosis) that resolve with or without medical intervention to grade 1 or less within this time frame. Toxicities for which further LMB-100 treatment should NOT be given are stated below in **Table 12**, which also provides guideline on how to manage some toxicities anticipated with LMB-100.

Event	Action to Be Taken
IRR/hypersensitivity reaction during administration of LMB-100	If an IRR/hypersensitivity develops, the infusion of LMB-100 should be temporarily interrupted. The participant should be monitored until complete resolution of the symptoms and treated as clinically indicated. Treatment or concomitant medication may include IV saline, oxygen, bronchodilators, corticosteroids, and vasopressors depending on the symptoms.
	 If the infusion is interrupted: In the event of IRR CTCAE Grade1, upon resolution of symptoms, the infusion will resume at the rate being used at the time that the IRR occurred In the event of IRR Grade 2 or 3, upon resolution of symptoms, the infusion will resume at one-half the previous rate. In the event of IRR CTCAE Grade 3 or Grade 4 (which may include pulmonary or cardiac events) or an anaphylactic reaction, the infusion should not be restarted, and the participant should receive aggressive treatment Participants experiencing IRR CTCAE Grade 4 or anaphylaxis must be permanently discontinued from study treatment For participants receiving LMB-100 who previously experienced IRR CTCAE ≥ Grade 2, the infusion rate for subsequent LMB-100 infusion should be reduced to one-half of the previous rate and corticosteroids premedication should be given 30 minutes prior to infusion in addition to standard pre-medications: Dexamethasone (20 mg PO 6 -12hrs before infusion or 8
	mg IV, $30 - 90$ min before infusion) or equivalent dose of another corticosteroid as clinically indicated
Capillary leak syndrome (CLS)	In the event of Grade 4 CTCAE capillary leak syndrome (urgent intervention indicated):

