For Grade 1-3 Capillary leak syndrome, the symptoms that make up this syndrome will be recorded separately, instead of classifying them as CLS.	 Vasopressor support (e.g., phenylephrine) if indicated to stabilize blood pressure Administer colloidal solutions (e.g., albumin) if there is a clinically significant, symptomatic and persistent systolic blood pressure drop, urine output significantly declines, or serum albumin falls to 2.5 mg/dL or lower
If the PI determines that the symptoms meet the definition of Grade 4 or 5 CLS, they will be recorded separately and CLS Grade 4 or 5 will also be recorded.	 For pulmonary congestion provide diuretic and/or albumin treatment as appropriate Progressive shortness of breath may require endotracheal intubation or drainage of a pleural effusion For oliguria and /or rising serum creatinine level delay LMB-100 if Grade 3 urine output decrease (<10 mL/hr)

Table 12. Guidelines for Managing LMB-100 Adverse Events

Event	Action to Be Taken			
	• Use dopamine if participant is unresponsive to or unable to tolerate fluids			
	• Manage pericardial effusion as outlined in section on "Inflammatory reactions to serosal membranes" below			
Inflammatory reactions to serosal membranes	 Hydrocortisone (200 mg IV) or a glucocorticoid equivalent as clinically indicated 			
	 o In the event of Grade ≥2 CTCAE pericardial effusion (asymptomatic effusion small to moderate size), consider delaying LMB-100 administration. In the event of Grade ≥3 CTCAE pericardial effusion (effusion with physiologic consequences) permanently discontinue LMB-100 treatment. Consult cardiology service for management recommendations which may include pericardial drainage. 			
	• In the event of pleuritis resulting in mild to severe pleuritic pain, treat with analgesics or steroids as clinically indicated			
	 For participants who have previously experienced pleuritis consider administration of dexamethasone 4 mg, PO bid beginning with first LMB-100 infusion and completing 24 hours after the last LMB-100 infusion of the cycle. (If participant is already receiving corticosteroids at dose and schedule at or above this amount as part of the pre-medication regimen, do not give additional steroids for pleuritis) 			
Dehydration	Encourage participants to maintain oral hydration (~1.5 L/ day)			
Nausea	Ondansetron or another anti-emetic should be available as needed			

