12.1.2.4 Risk of Capillary Leak Syndrome

LMB-100 administration may cause VLS characterized by hypotension, hypoalbuminemia, edema, weight gain, and hemoconcentration. Clinical trials with SS1P monotherapy have led to the development of reversible VLS. Participants will be monitored with frequent assessments of chest x-rays, weight, edema, blood pressure, and serum albumin levels prior to and during treatment. Participants who develop symptoms of VLS should be closely monitored and receive standard symptomatic treatments.

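### Serum albumin limits are printed in mg/dL instead of g/dL in inclusion criterion 2.1.1.10 and in the Table 12 colloid rule, so both are 1000 times too low

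*Combined protocol and SAP*

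**What the plan says.** Section 2.1.1, criterion 2.1.1.10, admits patients whose serum albumin is at least "2.5 mg/dL without intravenous supplementation". The criterion directly above it, 2.1.1.9, gives its blood-protein limit in grams: "hemoglobin ≥ 9 g/dL".

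Table 12 in Section 3.3.1 lists actions for capillary leak under the lead-in "In the event of Grade 4 CTCAE capillary leak syndrome (urgent intervention indicated". One bullet there gives colloid on any of three grounds: a significant, symptomatic and persistent fall in systolic pressure, a marked fall in urine output, or if "serum albumin falls to 2.5 mg/dL or lower".

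Section 3.1.3 (Treatment Extension) uses the entry limit a second time. It covers this situation: "If a participant chooses to defer treatment extension beyond 6 weeks or to have a different intervening therapy". The restart then requires washout periods and "criteria consistent with those described in Sections 2.1.1.8, 2.1.1.9 and 2.1.1.10".

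Albumin is measured at screening as part of the "Mineral Panel (albumin, calcium, magnesium, phosphorus" panel (Section 2.2.2). Section 12.1.2.4 calls for monitoring of "blood pressure, and serum albumin levels prior to and during treatment" but gives no threshold. No section states an albumin limit in g/dL.

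**The concern.** Serum albumin is normally a few grams per deciliter. A limit of 2.5 mg/dL is therefore not a low limit but one that no living patient could fall below. An entry floor that everyone clears is not a floor, and a trigger that no one can reach is not a trigger.

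Albumin matters for this drug. Section 1.2.8.1.1 reports hypoalbuminemia as the most common adverse event in the first LMB-100 trial (60.0%). Table 4 attributes it to LMB-100 in 9 of 13 patients, including 3 of 3 at 100 mcg/kg, which is dose level 1 here (Table 8). Section 12.1.2.4 lists it as a feature of the drug's vascular leak. Section 11.1 makes every patient who meets the Section 2.1 criteria eligible, and Section 9 has monitors confirm eligibility. With the printed unit, a monitor has no working numeric albumin limit to check against.

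**Working it through.** **Inputs**

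- Entry limit: at least 2.5 mg/dL (2.1.1.10).
- Colloid trigger: 2.5 mg/dL or lower (Table 12, Grade 4 capillary leak).
- Conversion: 1 g = 1000 mg.
- Assumption: patient albumin lies between 1.0 and 5.0 g/dL. The documents give no reference range, so this span is deliberately wide.

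The plan states the limit but does not derive it, so there is no calculation of the sponsor's to reproduce.

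**Conversion**

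- Printed limit: 2.5 mg/dL ÷ 1000 = 0.0025 g/dL.
- Corrected limit: 2.5 g/dL × 1000 = 2500 mg/dL.
- Ratio: 2500 ÷ 2.5 = 1000, the same in both places.
- Even the lowest assumed value is far above the printed limit: 1.0 ÷ 0.0025 = 400 times.

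**Applying both rules, as printed and as corrected**

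| Albumin (g/dL) | Meets entry limit, printed | Meets entry limit, g/dL | Colloid trigger, printed | Colloid trigger, g/dL |
|---|---|---|---|---|
| 1.0 | yes | no | no | yes |
| 1.5 | yes | no | no | yes |
| 2.0 | yes | no | no | yes |
| 2.5 | yes | yes | no | yes |
| 3.5 | yes | yes | no | no |
| 5.0 | yes | yes | no | no |

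As printed, both albumin columns are constant: everyone passes and the trigger never fires. In g/dL both rules separate patients at 2.5 g/dL. Of the three colloid triggers, one is disabled and two (blood pressure, urine output) are unaffected.

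**Is it a reading artifact?** The same unit appears in two separate sections, and the adjacent hemoglobin limit prints g/dL correctly. A fault in reading the PDF is therefore unlikely.

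**Does it touch the design?** No. The rule in Section 10.2 (11 or more of 15) has a probability of 5.92% if the true rate is 50% and 83.58% if it is 80%. These match the stated 5.9% and 83.6%, and neither uses albumin.

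**The case against.** The best case on the other side is that this is an obvious slip that would mislead no one. Patients are admitted to one center for LMB-100, a limit in mg/dL makes no physiological sense, and nothing is miscalculated from it. That is a fair argument about weight, and it is why the practical impact is put as small. It does not make the printed limits right.

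Four narrower points also deserve an answer.

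- **The supplementation qualifier in 2.1.1.10.** On a strict reading it might still keep out a patient receiving intravenous albumin. It more naturally says how the level must be reached, and in either case it does not restore a numeric floor.
- **Other routes to albumin in Table 12.** The table is guidance, and its next bullet allows albumin for pulmonary congestion with no threshold. That is true, but it is a separate indication. Together with the two remaining triggers, it means the clinical loss in Grade 4 leak is limited.
- **Discretion at restart.** Extension is at the investigator's discretion, and repeat screening evaluations may be required after a deferral. This is real cover, but it supplies no albumin value.
- **Toxicity-recovery rules.** Criterion 2.1.1.8 requires acute toxicities of prior treatment to be grade 1 or less, with listed exceptions, and Section 12.1.2 stops LMB-100 after a dose-limiting or treatment-limiting toxicity until recovery. Both depend on CTCAE 5.0 grading, which is not reproduced in the documents, so any albumin cut-offs it contains cannot be checked here. Both rules concern treatment toxicity, not low albumin from the cancer itself. Criterion 2.1.2.3 does reach such patients, but only through investigator judgment.

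**Conclusion.** The concern holds. Both numeric albumin limits in the documents are wrong as written by a factor of 1000 (0.0025 g/dL against 2.5 g/dL), and Section 3.1.3 inherits one of them. Read literally, the protocol has no working albumin floor at entry or at restart after a deferral, and one of the three colloid triggers in Grade 4 capillary leak cannot be met.

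The conclusion rests on the general fact that serum albumin is measured in grams per deciliter. It does not depend on the exact range, since even 1.0 g/dL is 400 times the printed limit. That 2.5 g/dL is the intended value is an inference, though hardly a doubtful one. How many patients a 2.5 g/dL limit would exclude cannot be stated, because the documents give no baseline albumin data.

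The practical impact is small, but these are operative safety rules, so the text should be corrected and not left to the reader to repair.

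**What to change.** Replace mg/dL with g/dL in criterion 2.1.1.10 and in the colloid bullet for capillary leak in Table 12. Section 3.1.3 refers to 2.1.1.10 by number and needs no edit of its own.

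The cost is two unit corrections. No visit, sample or test is added: albumin is in the screening Mineral Panel (Section 2.2.2), and the Study Calendar repeats that panel among the on-treatment labs. Sample size and analysis are unchanged.

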2.1.2 Exclusion Criteria

2.1.2.1 Known or clinically suspected CNS primary tumors or metastases including leptomeningeal metastases as CNS penetration of LMB-100 is expected to be poor. CNS

metastases are permitted if they have been previously treated, are asymptomatic, and have had no requirement for steroids or enzyme-inducing anticonvulsants in the last 14 days.

- 2.1.2.2 Evidence of significant, uncontrolled concomitant diseases which could affect compliance with the protocol or interpretation of results, including significant pulmonary disease other than that related to the primary cancer, uncontrolled diabetes mellitus, and/or significant cardiovascular disease (such as New York Heart Association Class III or IV cardiac disease, myocardial infarction within the last 6 months, unstable arrhythmias, unstable angina, or clinically significant pericardial effusion).
- 2.1.2.3 Any known diagnoses, metabolic dysfunction, physical examination finding, or clinical laboratory finding giving reasonable suspicion of a disease or condition (other than mesothelin [+] cancer diagnosis) that would contraindicate the use of an investigational drug, interfere with tumor measurement or lead to a life expectancy of less than 6 months as judged by the investigator.
- 2.1.2.4 Contraindication to receiving prophylactic doses of low-molecular weight heparin (LMWH) or direct oral anticoagulants (DOAC) such as current active bleeding (except for grade 1 hematuria or epistaxis), recent history of significant bleeding without subsequent effective medical or surgical intervention, known history of gastric varices, uncontrolled malignant hypertension, history of coagulopathy that confers increased risk of bleeding. Patients on concurrent treatment with anti-platelet agents such as aspirin or clopidogrel are eligible if deemed to have acceptable risk of bleeding in consultation with Hematologist. Patients already receiving prophylactic or therapeutic doses of anticoagulant (heparin-based or DOAC) for at least 4 weeks with no indication to this therapy.
- 2.1.2.5 Inability to administer or unwillingness to comply with recommended VTE prophylaxis for the duration of study treatment.
- 2.1.2.6 Prior diagnosis of hematologic malignancy
- 2.1.2.7 Active or uncontrolled infections (including tuberculosis, HIV, HBV, or HCV) or reasonable clinical suspicion of an active infection (such as cholangitis) as tofacitinib suppresses lymphocyte signaling and will impair host response to infection
- 2.1.2.8 Latent TB infection as identified by interferon-x release assay (IGRA). If IGRA is indeterminate, tuberculin skin test (TST) may be used to determine status.
- 2.1.2.9 Live attenuated vaccinations within 14 days prior to treatment.
- 2.1.2.10 Use of a strong inhibitor or inducer of CYP3A4 within 14 days prior to enrollment (see **Flockhart Table** (https://drug-interactions.medicine.iu.edu/Clinical-Table.aspx) or similarly updated source for a list of such agents)
- 2.1.2.11 Inability to take or digest oral medication.
- 2.1.2.12 Dementia or altered mental status that would prohibit informed consent.
- 2.1.2.13 Pregnant women are excluded from this study because the effects of LMB-100 and/or tofacitinib on the developing fetus are unknown and may have the potential to cause teratogenic or abortifacient effects. Because there is an unknown but potential risk for adverse events in nursing infants secondary to treatment of the mother with LMB-100

and/or tofacitinib, breastfeeding should be discontinued if the mother is treated with either of these agents.

- 2.1.2.14 Baseline QTcF interval of > 470 ms, participants with baseline resting bradycardia < 45 beats per minute, or baseline resting tachycardia >100 beats per minute.
- 2.1.2.15 Participants with contra-indication and/or history of severe hypersensitivity reactions to any components related to LMB-100 and tofacitinib.
- 2.1.2.16 Patients who have previously received LMB-100 (and therefore have high-levels of preexisting ADA's to drug)

2.1.3 Recruitment Strategies

Information about the study will be posted on sites such as clinicaltrials.gov and the CCR recruitment website. Information about the trial will also be distributed on NIH social media platforms. Subjects will also be drawn from patients seen in OP12 Medical Oncology clinic at the NIH Clinical Center as well as from referrals from outside providers.

2.2 SCREENING EVALUATION

2.2.1 Screening activities performed prior to obtaining informed consent

Minimal risk activities that may be performed before the subject has signed a consent include the following:

- Email, written, in person or telephone communications with prospective subjects
- Review of existing medical records to include H&P, laboratory studies, etc.
- Review of existing MRI, x-ray, or CT images
- Review of existing photographs or videos
- Review of existing pathology specimens/reports from a specimen obtained for diagnostic purposes
 - Archival tumor sample for NCI Laboratory of Pathology confirmation of diagnosis. A block of primary tissue (or 10 unstained sections on charged slides) from the time of diagnosis will be required from each participant. Tissue blocks from a known recurrence will be accepted if original tumor samples are unavailable. Referring institutions will send the tumor block or 10 unstained sections on charged slides to CCR/NCI for correlative studies and confirmation of diagnosis. A fresh biopsy may be collected if tumor tissue is not available.

2.2.2 Screening activities performed after a consent for screening has been signed

For patients requiring testing for MSLN expression (see Section 2.3.1), screening will occur on this study. For all other subjects, screening will occur on study 01-C-0129.

The following activities will be performed only after the subject has signed the appropriate consent for screening. They will be performed within 28 days before registration for study treatment unless specified:

- Assess tumor MSLN expression by immunohistochemistry analysis in archival tissue or fresh biopsy samples ONLY for patients who do not have a diagnosis of epithelioid mesothelioma, extrahepatic cholangiocarcinoma or pancreatic adenocarcinoma.
- Medical History and physical exam
- Vital signs including ambulatory oxygen saturation by pulse oximetry
- ECOG performance status
- Pregnancy test in women of childbearing potential (within 7-days prior to initiation of study therapy)
- ECG
- Echocardiogram
- CT scan of chest, abdomen and/or pelvis and areas of known or suspected disease involvement; MRI and/ or PET scan may also be performed when appropriate per PI discretion.
- CBC with differential, Acute Care Panel (sodium, potassium, chloride, bicarbonate, creatinine, glucose, BUN), Hepatic Panel (alkaline phosphatase, AST, ALT, total bilirubin, direct bilirubin), Mineral Panel (albumin, calcium, magnesium, phosphorus), creatine kinase, C-reactive protein, 1,25-dihydroxy vitamin D, Coagulation (PT, PTT), lactate dehydrogenase
- CA 19-9 serum tumor marker for pancreatobiliary cancer patients, or other appropriate tumor marker in other tumor types
- Testing for HIV, HCV, HBV: anti-HIV antibody, Anti-HCV Antibody, HBs Ag Screening
- Screening for latent tuberculosis by interferon-x release assay: QuantiFERON-TB Gold Plus or similar
- Urinalysis

